2.2.2 Dose Rationale

The proposed initial doses of 1, 2 and 5 µg for this FIH clinical study were chosen based on the PS levels contained in marketed PS conjugate vaccines and the ASP3772 nonclinical pharmacology and toxicology studies.

The 3 currently licensed pneumococcal conjugated vaccines vary in the number of serotypes they contain, the carrier proteins used and the methods of conjugation employed. The 7-valent formulation (Pfizer's Prevnar 7/Prevnar 7) with all serotypes conjugated to diphtheria toxoid mutant (CRM197), using a reductive animation conjugation method, was first licensed in the year 2000. The 10-valent formulation (GlaxoSmithKline Biologicals' Synflorix), with 8 serotypes conjugated to Protein D, a recombinant non-lipidated form of a highly conserved 40 kDa cell-surface lipoprotein of non-typeable *Haemophilus influenzae*, serotype 18C conjugated to tetanus toxoid and serotype 19F conjugated to diphtheria toxoid via bifunctional spacer, was licensed in Europe in 2009. The 13-valent formulation (Pfizer's PCV13/PCV13), with all serotypes conjugated to CRM197 using reductive animation, was licensed in 2010. In addition, Merck initiated the development of a 15-valent formulation (V114), using the PS dose ranges used previously by the commercially available pneumococcal conjugated vaccines. In all of these cases, the PS doses ranged from 1 μg to 4.4 μg for each of the serotypes. A nonclinical immunogenicity study with ASP3772 and PCV13 at one-tenth of the human PCV13 dose for each PS showed that ASP3772

serotype-specific responses to ASP3772 were comparable to those elicited by PCV13 for the 13 serotypes in common between the vaccines. For the 11 noncommon serotypes, there was a robust response elicited in rabbit for ASP3772 and no response for PCV13. In the toxicology study in New Zealand White rabbits, ASP3772 was administered at 5 µg of each of the 24 PS every 2 weeks, for a total of 5 intramuscular injections (5 cycles). The findings were mild in nature, and monitorable and reversible.

The above information, coupled with the literature showing successful translation between the rabbit immunogenicity studies and human efficacy for pneumococcal vaccines, support the position that ASP3772 has the potential to be clinically effective at the proposed doses (1 μ g, 2 μ g and 5 μ g).

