2.3 Endpoints

Stage 1:

Primary Endpoints

Safety and tolerability of ASP3772 will be assessed by:

- Treatment-emergent adverse events (TEAEs) including MAAEs, PIMMCs and NOCDs
- Vital signs (body temperature, blood pressure and pulse rate)
- Reactogenicity assessed using solicited adverse reactions recorded daily by the subject through day 7 postimmunization. These include local and systemic reactions with a predefined grading scale. Local reactions are pain, tenderness, redness/erythema and swelling/induration. Systemic reactions are nausea/vomiting, diarrhea, headache, fever, fatigue, and muscle discomfort or pain/myalgia. Joint pain/arthralgia through day 7 postimmunization will be assessed once by subject recall at the day 7 visit.

Additional safety assessments include laboratory values, ECGs and physical examinations.

Secondary Endpoints

Endpoints used to assess the immunological response on day 30 for the 13 serotypes contained in PCV13:

- Functional OPA activity for each serotype characterized by an OPA titer⁻¹ response expressed as the reciprocal of the serum dilution that causes a 50% reduction in the colony-forming units
- Pneumococcal serotype-specific anticapsular PS IgG for each serotype

Endpoints used to assess the immunological response on day 30 for the 11 serotypes unique to ASP3772:

- Geometric mean fold rise (GMFR) in anticapsular PS IgG at 30 days relative to pre-immunization
- Proportion of subjects with $a \ge 4$ -fold increase in anticapsular PS IgG
- Functional OPA activity expressed as an OPA titer-1

02 Dec 2019 Astellas Page 44 of 111

Stage 2 Group 2:

Primary Endpoints

Safety and tolerability of ASP3772 will be assessed by:

- TEAEs including MAAEs, PIMMCs, and NOCDs
- Vital signs (body temperature, blood pressure and pulse rate)
- Reactogenicity assessed using solicited adverse reactions recorded daily by the subject through day 7 postimmunization. These include local and systemic reactions with a predefined grading scale. Local reactions are pain, tenderness, redness/erythema and swelling/induration. Systemic reactions are nausea/vomiting, diarrhea, headache, fever, fatigue, joint pain/arthralgia and muscle discomfort or pain/myalgia.

Additional safety assessments include laboratory values, ECGs and physical examinations.

Secondary Endpoints

Endpoints used to assess the immunological response on day 30:

- Functional OPA activity for each serotype characterized by an OPA titer⁻¹ response

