6.1.2 Secondary Endpoint(s)

Stage 1, Group 1:

Surrogate markers used to assess the immunological response on day 30 for the 13 serotypes common to ASP3772 and PCV13 are:

- Functional OPA activity for each serotype characterized by an OPA titer⁻¹ response expressed as the reciprocal of the serum dilution that causes a 50% reduction in the colony-forming units
- Pneumococcal serotype-specific anticapsular polysaccharide PS IgG for each serotype.

Summaries of immune response 30 days after immunization in adults 18 to 64 years of age will be provided for each serotype by treatment group (ASP3772 (1 µg, 2 µg, 5 µg) or PCV13) and stage. All adult subjects treated with PCV13 will be combined into a single group. To assess similarity between the 3 cohorts of PCV13 subjects, summaries will be provided by cohort for the PS IgG levels and the OPA titers.

Endpoints used to assess the immunological response on day 30 for the 11 serotypes unique to ASP3772 (2, 8, 9N, 10A, 11A, 12F, 15B, 17F, 20B, 22F, 33F) are:

- Geometric mean fold rise (GMFR) in anticapsular PS IgG at 30 days relative to pre-immunization
- Proportion of subjects with a ≥ 4 -fold increase in anticapsular PS IgG
- Functional OPA activity for each serotype characterized by an OPA titer⁻¹ response

Stage 2; Group 2:

Endpoints used to assess the immunological response on day 30 are:

- Functional OPA activity for each serotype characterized by an OPA titer⁻¹ response
- Pneumococcal serotype-specific anticapsular PS IgG for each serotype for the 13 serotypes contained in PCV13
- For each of the 11 serotypes unique to ASP3772, the GMFR in anticapsular PS IgG at 30 days relative to pre-immunization
- For each of the 11 serotypes unique to ASP3772, the proportion of subjects with a ≥ 4 -fold increase relative to baseline in anticapsular PS IgG for ASP3772 and PCV13-treated subjects

For Stage 2, Group 2 summaries will be provided by treatment group (ASP3772 (1 μ g, 2 μ g, 5 μ g) or PCV13) for all subjects age 65-85, for subjects 65-74 and for those 75-85. Subjects treated with PCV13 in cohorts 4, 5 and 6 will be combined into a single dose group and summarized by age (65-85, 65-74 and 75-85). To assess similarity between the 3 cohorts of PCV13 subjects, summaries will be provided by cohort for the PS IgG levels and the OPA titers.

In addition, for ASP3772, the following endpoints will be assessed.

- Dose response in the OPA titer⁻¹ for ASP3772
- Dose response in the PS IgG antibodies for ASP3772

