7.4 Analysis of Immunogenicity

7.4.1 Analysis of Immunogenicity Endpoints

Assessment of immunological response following ASP3772 administration relative to PCV13 is a secondary objective for this study.

Stage 1, Group 1 and Stage 2, Group 2:

The objective in Stage 1, Group 1 and Stage 2, Group 2 is to determine if ASP3772 stimulates an immunogenic response to the 13 pneumococcal serotypes that are also contained in PCV13 and to determine if ASP3772 stimulates an immunogenic response to an additional 11 serotypes contained in ASP3772. The following summaries will be given by treatment group (ASP3772: 1, 2, 5 μ g vs. PCV13) and stage for all serotypes.

OPA Titer

- GMT, GSD and 95% CI
- The ratio of the OPA GMT (each ASP3772 dose level/PCV13), the GSD and 95% CI for the ratio
- The GMFR relative to baseline, GSD and 95% CI
- The proportion of subjects with a $>$ 4-fold increase in OPA titer¹

IgG Concentration

- The GMC, GSD and 95% CI
- The ratio of the IgG GMC (each ASP3772 dose level/PCV13), the GSD and 95% CI
- The GMFR relative to baseline, GSD and 95% CI
- The proportion of subjects with a \geq 4-fold increase in anticapsular PS IgG

Values below the LLOQ will be set to $\frac{1}{2}$ LLOQ for calculation of geometric means and set to LLOQ for calculation of fold changes.

Summaries for Stage 2 subjects will be given for 65-85, 65-74 and 75-85-year olds.

An analysis of covariance (ANCOVA) model with age (65 to 74 years, 75 to 85 years) as the covariate and treatment (ASP3772 1, 2, 5 μ g) as the factor of interest will be conducted on the natural logarithm (log) of pneumococcal OPA titers and on the natural log of the IgG concentrations for each serotype to examine dose response. Provided the treatment effect is

significant, paired comparisons between the 5 μ g vs 1 μ g, followed by 5 μ g vs 2 μ g, followed by 2 μ g vs 1 μ g will be conducted. There are no adjustments to control for the Family-Wise Error Rate (FWER) for 3 comparisons for each of the 24 serotypes. A Cochran-Armitage trend test will be used to test for trend.

CCI

Stage 2; Group 3:

The objective for Stage 2, Group 3 is to obtain estimates of the immune response following PPSV23 for the 11 serotypes contained in PPSV23 and not in PCV13. Immunological response 30 days after administration of PPSV23 will be summarized as follows:

- The GMT, GSD and 95% CI for the OPA titers
- The GMC, GSD and 95% CI for serotype-specific IgG levels.

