Proportion of subjects with a > 4-fold increase in OPA titer

SAS PROC FREQ can be used to obtain the proportions and 95 % CI for each serotype.
PROC FREQ data=xxxx order=freq;

```
tables fourfold / binomial (wilson) alpha=0.05;  
weight count;
```

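### The Appendix A template for the 4-fold OPA responder proportion estimates whichever outcome is commoner, so where fewer than half respond it yields the non-responder rate and interval.

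*SAP*

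**What the plan says.** The last block of SAP Appendix A (10.1) is headed "Proportion of subjects with a > 4-fold increase in OPA titer". It states that "SAS PROC FREQ can be used to obtain the proportions and 95 % CI for each serotype" and gives three statements: "PROC FREQ data=xxxx order=freq", then "tables fourfold / binomial (wilson) alpha=0.05", then a WEIGHT statement for the cell counts. It has no LEVEL= option and no BY statement, and it does not say how the variable `fourfold` is coded.

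SAP 7.4.1 asks for responder proportions for both OPA and IgG, by treatment group "and stage for all serotypes", and for both assays again in Group 3. The responder endpoint that SAP 6.1.2 and Protocol 2.3 list as secondary is the IgG one, for the 11 serotypes unique to ASP3772. For Stage 2, SAP 6.1.2 specifies it "in anticapsular PS IgG for ASP3772 and PCV13-treated subjects". No other responder-rate code appears in the SAP.

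**The concern.** The heading asks for the proportion with the increase, but the code does not tie the estimate to that outcome. In PROC FREQ, ORDER=FREQ sorts levels by descending count, and BINOMIAL without LEVEL= estimates the first level listed. Together they return the proportion for the commoner outcome. That is the responder rate in high-responding cells and the non-responder rate in low-responding ones, decided cell by cell by the data.

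Such an error differs between arms: a low arm is flipped and a high arm is left alone, so a difference can shrink, vanish or reverse. If the template is reused for IgG, the most exposed cells are PCV13 recipients on the 11 serotypes that PCV13 lacks. Low rates are the natural expectation there. Protocol 2.2.2 reports from the nonclinical work: "For the 11 noncommon serotypes, there was a robust response elicited in rabbit for ASP3772 and no response for PCV13".

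**Working it through.** The plan states no responder rate, power or precision for this endpoint, so there is no figure to reproduce. The code was traced by hand; SAS was not run.

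**Inputs from the documents.** Stage 2 Group 2: 99 per ASP3772 dose; PCV13 pooled 3 × 33 = 99. Stage 1: 30 per dose; PCV13 pooled 3 × 10 = 30 (SAP 3.2). Wilson limits, two-sided 95% (Appendix A).

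**Assumptions.** All responder counts and true rates below are illustrative, since the documents give none. The code is run once per arm and serotype, as SAP 7.4.1 implies.

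**Step 1: what is printed.** With r responders among n, the first level under ORDER=FREQ has count max(r, n − r), so the printed estimate is max(r, n − r)/n. The intended estimate is r/n. The printed value can never be below 50%.

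**Step 2: Wilson interval.** Centre = (p + z²/2n)/(1 + z²/n); half-width = z√[p(1 − p)/n + z²/4n²]/(1 + z²/n), with z = 1.96. For r = 2, n = 99 the code uses p = 97/99 = 0.980. The centre is 0.962 and the half-width 0.033, giving 92.9% to 99.4%.

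| n | Responders | Printed by the template | Intended |
|---|---|---|---|
| 99 | 2 | 98.0% (92.9–99.4) | 2.0% (0.6–7.1) |
| 99 | 20 | 79.8% (70.8–86.5) | 20.2% (13.5–29.2) |
| 99 | 30 | 69.7% (60.0–77.9) | 30.3% (22.1–40.0) |
| 99 | 40 | 59.6% (49.7–68.7) | 40.4% (31.3–50.3) |
| 99 | 80 | 80.8% (72.0–87.4) | the same |
| 30 | 3 | 90.0% (74.4–96.5) | 10.0% (3.5–25.6) |
| 30 | 6 | 80.0% (62.7–90.5) | 20.0% (9.5–37.3) |

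**Step 3: how often a cell flips.** A cell flips when r < n/2. The probability is the binomial P(r ≤ 49) for n = 99 and P(r ≤ 14) for n = 30.

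| True rate (assumed) | n = 99 | n = 30 |
|---|---|---|
| 20% | >0.999 | >0.999 |
| 30% | >0.999 | 0.983 |
| 40% | 0.978 | 0.825 |
| 45% | 0.841 | 0.645 |
| 55% | 0.159 | 0.231 |
| 60% | 0.022 | 0.097 |

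**Step 4: effect on a dose pattern.** Suppose 30, 50 and 70 of 99 respond at the three doses. The intended rates are 30.3%, 50.5% and 70.7%. The template prints 69.7%, 50.5% and 70.7%, so a rising pattern becomes a U-shape.

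**Step 5: empty cells.** WEIGHT without ZEROS drops a zero-count row. An arm with no responders then shows a single level at 100%.

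**The case against.** A reader might infer that the trial's tables will report non-responder rates as responder rates, or that the SAP inverts its listed secondary endpoint. The documents do not support either.

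- The block is a template. It says PROC FREQ can be used, names a placeholder dataset and leaves the variable uncoded. The estimand is explicit in the heading and in SAP 7.4.1.
- PROC FREQ output tabulates both levels and labels the level behind the binomial block. A wrong figure reaches a table only if someone copies from that block without checking the label. SAP 7.4.1 asks for proportions and, for Group 3, numbers and percentages, which the frequency table gives under any ordering.
- Table formats sit in separate TLF specifications (SAP 7.1), and a review of data and TLFs precedes hard lock (SAP 1).
- The heading covers OPA. The listed responder endpoint is IgG, so applying the code there is an inference, resting on the absence of any other code.
- For serotypes unique to ASP3772, SAP 7.1 makes the comparison post-dose against pre-dose, so PCV13 is not the stated contrast. SAP 7.4.1 also requires the fold rise by arm, and a very high PCV13 responder rate beside a fold rise near 1 would look contradictory.
- No test or decision rule is set on responder proportions. The primary endpoints are safety, and the dose-response ANCOVA uses log titres and log concentrations.

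All of this stands, and it limits the consequence. It does not repair the code. The Wilson interval comes from the block that flips, nothing in the SAP fixes the level, and a second programmer following the same appendix would reproduce the result. Detection would depend on someone noticing.

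**Conclusion.** The template is wrong as written. Where fewer than half of an arm respond to a serotype, its binomial estimate and Wilson interval describe non-responders. At n = 99 this is near certain for true rates of 30% or less and has probability 0.84 at 45%. It leaves cells at or above 50% unchanged.

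The conclusion rests on standard PROC FREQ defaults, which the documents do not restate, and on running the code by arm and serotype. The magnitudes rest on assumed responder rates. The defect is established for the OPA template; for IgG it follows only if the code is reused. Because the affected items are descriptive secondary summaries and the output could expose the flip, this is a should-fix correction. It does not threaten the design or any stated test.

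**What to change.** In Appendix A:

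1. Delete `order=freq`.
2. State how `fourfold` is coded and which value means responder. The coding should also say whether an exactly 4-fold rise counts. That is a separate matter: the SAP uses a strict inequality for OPA in Appendix A and in the Groups 1 and 2 list, but at-least-4-fold for IgG.
3. Name the level: `binomial(level=<responder value> wilson)`. The value must match the stated coding; a literal such as 'Y' should not be assumed, because the SAP gives no coding.
4. Keep empty cells by including an explicit zero-count row in the input and using `weight count / zeros`. The option does nothing if the row is absent.
5. State that the code covers OPA and IgG responders in Groups 1, 2 and 3, run by arm and serotype.

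The cost is a few lines of SAP text. Estimates and intervals for cells at or above 50% do not change, and no data collection or sample size is affected.

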10.2 Appendix B: Local Reactogenicity Grading

Stage 1 Group 1 and Stage 2 Group 2 subjects will record the local reactogenicity in an electronic diary along with body temperature through day 7 following study immunization.

Local Reaction to Injectable Product	Mild (Grade 1)	Moderate (Grade 2)	Severe (Grade 3)	Potentially Life-threatening (Grade 4)
Pain	Does not interfere with activity	Repeated use of non-narcotic pain reliever > 24 hours or interferes with activity	Any use of narcotic pain reliever or prevents daily activity	ER visit or hospitalization
Tenderness	Mild discomfort to touch	Discomfort with movement	Significant discomfort at rest	ER visit or hospitalization
Erythema/Redness†	2.5 – 5 cm	5.1 – 10 cm	> 10 cm	Necrosis or exfoliative dermatitis
Induration/Swelling‡	2.5 – 5 cm and does not interfere with activity	5.1 – 10 cm or interferes with activity	> 10 cm or prevents daily activity	Necrosis

ER: emergency room

† In addition to grading the measured local reaction at the greatest single diameter, the measurement should be recorded as a continuous variable. A measurement tool will be provided to the subjects to measure the size of the erythema/redness.

‡ Induration/Swelling should be evaluated and graded using the functional scale, as well as the actual measurement. A measurement tool will be provided to the subjects to measure the induration/swelling.

10.3 Appendix C: Grading Signs of Systemic Reactogenicity

Vital signs measurements will be monitored for reactogenicity through 1 hour postdose in all Stage 1 Group 1 and Stage 2 Group 2 subjects. Oral temperature will be recorded by the subjects daily through day 7 post immunization.

Table C1.

Vital Signs†	Mild (Grade 1)	Moderate (Grade 2)	Severe (Grade 3)	Potentially Life-threatening (Grade 4)
Fever (°C)‡ (°F)‡	38.0 – 38.4 100.4 – 101.1	38.5 – 38.9 101.2 – 102.0	39.0 – 40 102.1 – 104	> 40 > 104
Tachycardia (bpm)	101 – 115	116 – 130	> 130	ER visit or hospitalization for arrhythmia
Bradycardia (bpm)§	50 – 54	45 – 49	< 45	ER visit or hospitalization for arrhythmia
Hypertension (systolic) (mm Hg)	141 – 150	151 – 155	> 155	ER visit or hospitalization for malignant hypertension
Hypertension (diastolic) (mm Hg)	91 – 95	96 – 100	> 100	ER visit or hospitalization for malignant hypertension
Hypotension (systolic) (mm Hg)	85 – 89	80 – 84	< 80	ER visit or hospitalization for hypotensive shock
Respiratory Rate (breaths per min)	17 – 20	21 – 25	> 25	Intubation

bpm: beats per minute; ER: emergency room

† Subject should be at rest for all vital sign measurements.

‡ Oral temperature; no recent hot or cold beverages or smoking. Subjects will be provided with an oral thermometer to record temperature daily through day 7 postimmunization.

§ When resting heart rate is between 60 and 100 bpm. Use clinical judgment when characterizing bradycardia among some healthy subject populations, e.g., conditioned athletes.

Table C2.

	Absolute change to include in calculations
Fever (°C)‡	As in Table above (change in Grade)
Tachycardia (bpm)	As in Table above (change in Grade)
Bradycardia (bpm)§	>10 bpm
Hypertension (systolic) (mm Hg)	>20 mmHg
Hypertension (diastolic) (mm Hg)	>15 mmHg
Hypotension (systolic) (mm Hg)	As in Table above (change in Grade)
Respiratory Rate (breaths per min)	>4 breaths/min

Stage 1 Group 1 and Stage 2 Group 2 subjects will be asked to record the below systemic reactogenicity symptoms through day 7 following study immunization.

Table C3.

Systemic (General)	Mild (Grade 1)	Moderate (Grade 2)	Severe (Grade 3)	Potentially Life-threatening (Grade 4)
Nausea/ Vomiting	No interference with activity or 1 – 2 episodes/24 hours	Some interference with activity or > 2 episodes/24 hours	Prevents daily activity, requires outpatient IV hydration	ER visit or hospitalization for hypotensive shock
Diarrhea	2 – 3 loose stools or < 400 g/24 hours	4 – 5 stools or 400 – 800 g/24 hours	6 or more watery stools or > 800 g/24 hours or requires outpatient IV hydration	ER visit or hospitalization
Headache	No interference with activity	Repeated use of non-narcotic pain reliever > 24 hours or some interference with activity	Significant; any use of narcotic pain reliever or prevents daily activity	ER visit or hospitalization
Fatigue	No interference with activity	Some interference with activity	Significant; prevents daily activity	ER visit or hospitalization
Arthralgia*	No interference with activity	Some interference with activity	Significant; prevents daily activity	ER visit or hospitalization
Myalgia	No interference with activity	Some interference with activity	Significant; prevents daily activity	ER visit or hospitalization
Illness or clinical AE (as defined according to applicable regulations) †	No interference with activity	Some interference with activity not requiring medical intervention	Prevents daily activity and requires medical intervention	ER visit or hospitalization

AE: adverse event; ER: emergency room; IV: intravenous.

*: Stage 1, subjects will be questioned on day 7 visit if they experienced any join pain/arthritis through day 7 and if yes, the site personnel will report it as a clinical event using this grading scale. Stage 2 subjects will report Arthralgia daily on electronic diary through day 7.

† : Subjects will be questioned on day 7 if they experienced any other illness through day 7 post immunization and if any site personal will report it as a clinical event using this grading scale.

10.4 Appendix D: Grading Laboratory Abnormalities for Healthy Adult Subjects

Clinical laboratory test results will be graded and displayed using these grades. Grading values are based on ICON Central Laboratories, and will be adjusted if the reference ranges change.

Chemistry	ICON Reference range	Mild (Grade 1)	Moderate (Grade 2)	Severe (Grade 3)	Potentially Life-threatening (Grade 4)†
Sodium – Hyponatremia (mEq/L)	136-145*	133 – 135	131 – 132	126 – 130	< 126
Sodium – Hypernatremia (mEq/L)		146 – 147	148 – 149	150 – 151	> 151
Potassium – Hypokalemia (mEq/L)	3.5-5.1*	3.3 – 3.4	3.1 – 3.2	2.9 – 3.0	< 2.9
Potassium – Hyperkalemia (mEq/L)		5.2 – 5.3	5.4 – 5.5	5.6 – 5.7	> 5.7
Glucose – Hypoglycemia (mg/dL)		60 – 64	50 – 59	40 – 49	< 40
Glucose – Hyperglycemia	Fasting 74-99	100 – 110	111 – 125	> 125	Insulin requirements or hyperosmolar coma
Fasting (mg/dL)					
Random (mg/dL)	Random 74-139	140 – 155	156 – 230	> 230	
Blood Urea Nitrogen (mg/dL)	7-19 (F) [18-50] 10-20 (F) [>50] 9-21 (M) [18-50] 8-26 (M) [>50]	22 – 25	26 – 30	> 30	Requires dialysis
Creatinine (mg/dL)	0.55-1.02 (F) 0.72-1.18 (M)	1.5 – 1.7	1.8 – 2.1	2.2 – 2.5	> 2.5 or requires dialysis
Calcium – Hypocalcemia (mg/dL)	8.4-10.2	7.9 – 8.3	7.4 – 7.8	6.9 – 7.3	< 6.9
Calcium – Hypercalcemia (mg/dL)		10.3 – 11.0	11.1 – 11.5	11.6 – 12.0	> 12.0
Magnesium – Hypomagnesemia (mg/dL)	1.3-2.1*	1.1-1.2	0.9 – 1.0	0.7 – 0.8	< 0.7
Phosphorous – Hypophosphatemia (mg/dL)	2.3-4.7	2.0 – 2.2	1.7 – 1.9	1.3 – 1.6	< 1.3
Creatine Kinase (mg/dL)	29-168 (F) 30-200 (M)	1.25 – 1.5 × ULN***	1.6 – 3.0 × ULN	3.1 – 10 × ULN	> 10 × ULN
Albumin – Hypoalbuminemia (g/dL)	3.5-5.0 [18-61] 3.4-4.8 [>61]	2.8 – 3.1	2.5 – 2.7	< 2.5	NA
Total Protein – Hypoproteinemia (g/dL)	6.4-8.3	5.5 – 6.0	5.0 – 5.4	< 5.0	NA
ALP (Increase by Factor)	40-150	1.1 – 2.0 × ULN	2.1 – 3.0 × ULN	3.1 – 10 × ULN	> 10 × ULN
Liver Function Tests – ALT (Increase by Factor)	≤55	1.1 – 2.5 × ULN	2.6 – 5.0 × ULN	5.1 – 10 × ULN	> 10 × ULN
Liver Function Tests – AST (Increase by Factor)	5-34	1.1 – 2.5 × ULN	2.6 – 5.0 × ULN	5.1 – 10 × ULN	> 10 × ULN
Bilirubin – When Accompanied by Any Increase in Liver Function Test (Increase by Factor)	≤1.20	1.1 – 1.25 × ULN	1.26 – 1.5 × ULN	1.51 – 1.75 × ULN	> 1.75 × ULN
Bilirubin – When Liver Function Test is Normal (Increase by Factor)	≤1.20	1.1 – 1.5 × ULN	1.6 – 2.0 × ULN	2.0 – 3.0 × ULN	> 3.0 × ULN

Table continued on next page

Chemistry	ICON Reference range	Mild (Grade 1)	Moderate (Grade 2)	Severe (Grade 3)	Potentially Life-threatening (Grade 4)†
Total Cholesterol (mg/dL)	Desirable: < 200 mg/dL Borderline: 200 – 239 mg/dL High: ≥ 240 mg/dL	201 – 210	211 – 225	> 226	NA

* The laboratory values provided in the tables serve as guidelines and are dependent upon institutional normal parameters. Institutional normal reference ranges should be provided to demonstrate that they are appropriate.

** The clinical signs or symptoms associated with laboratory abnormalities might result in characterization of the laboratory abnormalities as Potentially Life Threatening (Grade 4). For example, a low sodium value that falls within a grade 3 parameter (125-129 mE/L) should be recorded as a grade 4 hyponatremia event if the subject had a new seizure associated with the low sodium value.

***ULN" is the upper limit of the normal range.

ALP: alkaline phosphatase; ALT: alanine aminotransferase; AST: aspartate aminotransferase; NA: not applicable; ULN: upper limit of normal

Hematology	ICON Reference range	Mild (Grade 1)	Moderate (Grade 2)	Severe (Grade 3)	Potentially Life-threatening (Grade 4)
Hemoglobin (Female Subjects) (g/dL)	11.5-15.5	10.0 – 10.9	8.5 – 9.9	7.0 – 8.4	< 7.0
Hemoglobin (Female Subjects) Change From Baseline Value (g/dL)		Any decrease – 1.5	1.6 – 2.0	2.1 – 5.0	> 5.0
Hemoglobin (Male Subjects) (g/dL)	13.2-17.0	11.4 – 12.4	10.0 – 11.3	8.0 – 9.9	< 8.0
Hemoglobin (Male Subjects) Change From Baseline Value (g/dL)		Any decrease – 1.5	1.6 – 2.0	2.1 – 5.0	> 5.0
White Blood Cell Increase (k/uL)	3.50-11.10*	11 – 15	15.1 – 20	20.1 – 25	> 25
White Blood Cell Decrease (k/uL)	3.50-11.10*	2.5 – 3.5	1.5 – 2.4	1 – 1.4	< 1
Lymphocytes Decrease (k/uL)	1.2-4.0	0.5 - 0.6	0.3 - 0.4	0.1 - 0.2	< 0.1
Neutrophils Decrease (k/uL)	1.8-7.0	1.3 - 1.6	0.8 - 1.2	0.5 - 0.7	< 0.5
Eosinophils (k/uL)	0.0-0.5	0.8 – 1.2	1.3 - 5	> 5	Hypereosinophilic
Platelets Decreased (k/uL)	150-400	125 – 140	100 – 124	25 – 99	< 25
Prothrombin Time (Increase by Factor)	11.4-14.9 sec	1.01 – 1.10 × ULN†	1.11 – 1.20 × ULN	1.21 – 1.25 × ULN	> 1.25 ULN
Partial Thromboplastin Time (Increase by Factor)	24.7-34.4 sec	1.01 – 1.2 × ULN	1.21 – 1.4 × ULN	1.41 – 1.5 × ULN	> 1.5 × ULN
Fibrinogen Increase (mg/dL)	228-439	476 – 600	601 – 700	> 700	NA
Fibrinogen Decrease (mg/dL)		150 – 199	125 – 149	100 – 124	< 100 or associated with gross bleeding or DIC

* The laboratory values provided in the tables serve as guidelines and are dependent upon institutional normal parameters. Institutional normal reference ranges should be provided to demonstrate that they are appropriate.

DIC: disseminated intravascular coagulation; NA: not applicable; ULN: upper limit of normal

† Upper limit of the normal range.

Urine	ICON Reference range	Mild (Grade 1)	Moderate (Grade 2)	Severe (Grade 3)	Potentially Life-threatening (Grade 4)
Protein	Negative	Trace	1+	2+	Hospitalization or dialysis
Glucose	Negative	Trace	1+	2+	Hospitalization for hyperglycemia
Blood (Microscopic) – RBC per HPF (rbc/hpf)	None	1 - 10	11 – 50	> 50 and/or gross blood	Hospitalization or packed RBC transfusion

RBC: red blood cell; HPF: high power field

